Setting: Screening, baseline, outcome testing and intervention meetings will be conducted at the Sarah W. Stedman Center for Nutritional Studies on the Center for Living Research and Wellness campus at Duke University. Diet and exercise classes will be offered virtually via WebEx or in person at the Center for Living campus. Anthropometrics, functions tests, and blood collection will take place in the Clinical Research Unit there or may be conducted virtually if needed. The Isokinetic knee extension peak torque testing and BodPod body composition measurements will be done in the Sports Sciences Institute, which is adjacent to the Stedman Building. The thigh CT scans will be conducted in Radiology at the Veterans Affairs Medical Center in Durham.

We will enroll participants until we reach a total of 112 study completers. We anticipate enrolling approximately 160, allowing for a 30% dropout rate.

Study Arms:

- **Arm 1: WL-Control (n=56 completers)**
10%* WL diet with 0.8 g protein/kg body wt/day
- **Arm 2: WL-Pro (n=56 completers)**
10%* WL diet 1.4 g protein/kg body wt/day; \geq 30g high quality protein per meal

**Participants enrolled after 10/1/2023 will participate in a shortened study period of 3 months, with only 0 and 3 month assessments for most measures, as noted in the added footnotes below. Their weight loss prescription will be targeted to an expectation of at least 5-10% loss of body weight.*

Measurements:

After the participant has been consented and HIPAA Authorization forms have been signed, screening and baseline assessments will be conducted:

Screening process:

Screening Visit : Consent; confirm BMI ≥ 30 kg/m², confirmed SPPB score of 4-11, confirmed fasting plasma glucose ≥ 95 and < 126 mg/Dl or A1c between 5.7-6.4 (will be confirmed with LapCorp results), and confirmed Mini-Cog score ≥ 3 (if less than 3, confirm participant can conduct all ADLs).

Upon the completion of all baseline assessments (see below), the study biostatistician will then use permuted-block randomization to assign participants to WL-Control or WL-Protein groups. The following variables will be blocked in this order: 1) Race (white versus non-white, 2) Couple/Single status. An equal number of participants will be randomized across the two arms to end up with N=84 (42 black and 42 white) in each arm.

Measures and Data Collection Points

Primary outcome: Physical function (SPPB)

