This design is a two-armed clinical trial, with replicate measures at three time points: baseline, three, and six months. Since subjects are randomized to either WL-Control or WL-Protein arm, and the groups are presumed equal at baseline, the analysis is straightforward. Following the Good Clinical Practice Guidelines for the analysis of a clinical trial, we will employ mixed models, analyze under an Intent to Treat (ITT) criteria, and control for baseline and assess the impact of Time, Treatment Group and the interaction of these variables on the outcomes. Relative to the usual repeated measures designs, mixed models have several advantages: 1) missing values present no particular difficulties in estimation and the estimates are unbiased as long as the set of variables leading to MAR are estimated, 2) the usual assumption of conditional independence (compound symmetry) used in standard repeated measures need not be made, and 3) the actual times of measurement need not be equivalent across subjects. Controlling for the individual baseline values for the particular outcomes, the trajectories over time and differences in those trajectories will be assessed. Following the statistical principles section from the International Conference on Harmonization, we will select covariates (e.g., age, race, number of comorbidities) for the primary models a priori, but we also will conduct auxiliary sensitivity analyses that evaluate whether potential group imbalances bias the treatment effect estimate. These analyses will be performed using conventional testing for confounding. We note that we have listed numerous measures to be analyzed as outcomes, but have listed only 1 primary outcome (physical function, Aim 1).

For any particular outcome, the general form of the model will be:

$$Y_{it} = \beta_0 + \beta_1(\text{group}) + \beta_2(\text{time}_t) + \beta_3(\text{group} * \text{time}_t) + \beta_4(\text{covariates}) + \epsilon_{it}$$

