In addition to the impact of the intervention on the secondary outcomes, we will assess mediation of the group effect on the primary outcome by demographic, comorbid and adherence variables. Subjects may differ in their process of change depending on baseline demographic and functional status values. Second, we will assess the functional form of the change over time, by looking at non-linear functions of change. For example, change in function and performance is likely to be non-linear, initially changing quickly and leveling at points distal from baseline. It would be important to note if this change differed by group. Finally, we will assess whether the trajectories of change, irrespective of group assignment, are similar for individuals. In this application, we have listed several variables, which we expect to change as result of the intervention. We further hypothesize that all these variables will change in the same pattern. To test this hypothesis, across the range of outcome measures, we can look at overall change through the use of multivariate tests (Boc⁵⁹ or Anderson⁶⁰) for the singly measured functional items, and by assessment of correlated trajectories for those outcomes measured repeatedly. With appropriate weighting for number of observations per individuals, the correlation between individual trajectories can be assessed. A positive correlation between the trajectories for any two outcomes will indicate that the subjects changed similarly for the 2 outcomes, and will provide

additional support for the notion that the intervention had a generalized effect across the outcomes. Significant correlations would perhaps indicate mechanistic/causal linkage between variables over time, or, from a reliability standpoint, may indicate that the subsequent trial may want to employ summary measures aggregating across outcome measures, or, alternatively, employ multivariate tests across several outcomes to assess the group differences, reducing the chance of Type-I error inherent in the testing of multiple variables. We will not adjust for Type-I error rate for these secondary outcomes.

Analysis Plan (Aim 3):

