Primary outcome data collected during the trial will be analyzed for differences due to race. Using the same analytic strategy listed in the analysis of Aims 1 and 2, race (B/W) will be included into the analytic structure for the physical function (SPPB) outcome, first as a main effect (mediating), and secondly, as an interaction (moderating) with group. If the physical function change outcome is normally distributed, we will employ, 2-way ANCOVA, with race and group serving as factors, and controlling for baseline physical function. While our working hypotheses are directional, our tests will be two-tailed. If physical function is not distributed approximately normal, we will attempt to assess the outcome using appropriate transformations, or bootstrapping simulations⁶¹. We are aware race and compliance may be partially confounded. As a final sensitivity analysis, we will assess if any observed relationships are mediated by compliance with the protocol. Next secondary outcomes data collected will be used to test the hypotheses about racial differences. Preliminarily, we will assess if the distributional assumptions of the outcomes of the ANCOVA model are met. If not, we will attempt to delimit an appropriate transformation, or employ bootstrapping. To assess the racial effects, the change of these outcomes by intervention group and race will be assessed, controlling for the baseline levels. Both the interactive (with group) and the main effects of race and group will be assessed. In addition, we will assess if the race effects are mediated by compliance. We will not control for the Type-I error rate inherent in multiple testing of multiple outcomes. Rather, for any relationship declared statistically significant, the reader will be alerted to the preliminary nature of the findings, the multiple testing issues and the requirement for replication. The results of these analyses will provide invaluable information regarding the process and functional forms and, potentially, the causal pathways of the intervention process. For example, one important analysis will enter 'level of compliance to the intervention' into the analysis, allowing for a 'per protocol' analysis of the results.

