Aim 2 and 3: This design is a two-armed feasibility trial, with replicate measures at three time points: baseline, three, and six months. Since subjects are randomized to either HR-WL-Protein or HR-WL-Control, and the groups are presumed equal at baseline, we will employ mixed models, analyze under an Intent to Treat (ITT) criteria, and control for baseline and assess the impact of Time, Treatment Group and the interaction of these variables on the outcomes. Controlling for the individual baseline values for the particular outcomes, the trajectories over time and differences in those trajectories will be assessed. Following the statistical principles section from the International Conference on Harmonization, we will select covariates (e.g., age, race, number of comorbidities) for the primary models a priori, but we also will conduct auxiliary sensitivity analyses that evaluate whether potential group imbalances bias the treatment effect estimate. These analyses will be performed using conventional testing for confounding. As defined, the overall test of the intervention effect will be the joint effect of group and group*time on 2 df assessing an overall effect of group, and if this group effect is constant over time. If significant, follow-up tests will assess where group differences lie. In particular, we note that if the time by group interaction is rejected, we will test if the groups differ at the end of 6 months (a test of effect at the completion of the intervention). We will carefully examine model assumptions, including the distribution of model residuals, additively, linearity, and influential observations, and will, if necessary, re-parameterize the models or transform the outcomes accordingly.

Privacy, Confidentiality, and Information Security

Lists of Data Reviewed and/or Collected for Screening/Recruitment and Conduction of Study:

- Demographics: age, race, gender, weight, height, marital status, education, employment status, living arrangements, socioeconomic and smoking status
- Diagnosis of pre-diabetes
- Mini Cog
- Hand-grip strength
- Weight
- Height
- Physical Function – Short physical performance battery, 6-minute walk, 30 second chair stand, 8 foot up and go
- Physical activity – Actigraph and wear log
- CT-scan of the thigh

- Isokinetic knee extensor peak torque
- Three-day food record
- Protein checklist
- Nutrition Literacy Questionnaire
- Food Security Questionnaire
- Intervention Evaluation Questionnaire

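### Mediation of the diet effect is planned through demographic and comorbid variables; those fixed before randomisation cannot mediate it, and the moderation question actually posed gets no interaction test except for race

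*Combined protocol and SAP*

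**What the plan says.** The Analysis Plan for the parent protocol (Aims 1 and 2) adds this to the primary and secondary analyses: "we will assess mediation of the group effect on the primary outcome by demographic, comorbid and adherence variables". The reason given is: "Subjects may differ in their process of change depending on baseline demographic and functional status values".

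The same plan relies on randomisation for comparability: "Since subjects are randomized to either WL-Control or WL-Protein arm, and the groups are presumed equal at baseline, the analysis is straightforward". It also uses variables of the same kind for adjustment: "we will select covariates (e.g., age, race, number of comorbidities) for the primary models a priori". Its general model contains group, time, group by time and a vector of covariates. It has no product of group with a covariate.

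The Analysis Plan (Aim 3) brings race into the model "first as a main effect (mediating), and secondly, as an interaction (moderating) with group". Later it uses the word in another sense, for compliance: "we will assess if any observed relationships are mediated by compliance with the protocol". Under Design, randomisation is stratified: "The following variables will be blocked in this order: 1) Race (white versus non-white, 2) Couple/Single status".

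The data list in the privacy section shows what counts as demographic: "Demographics: age, race, gender, weight, height, marital status, education, employment status", and further items. No section defines mediation or gives a mediation model.

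**The concern.** A mediator lies on the path from treatment to outcome, so treatment must be able to change it. Diet assignment cannot change age, education or a comorbidity count taken at entry. Of the three classes the sentence names, adherence plainly arises after randomisation. The other two are, as far as the documents show, mainly baseline characteristics.

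The stated reason is about something else: whether response depends on where a participant starts. That needs a group-by-variable interaction. Two things are at stake. A mediation analysis run on baseline variables could present arm imbalance as a mechanism. And the question of who benefits, which the protocol raises itself, would go untested for every variable except race.

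**Working it through.** **1. The plan's own figures.** The plan attaches no number to the mediation analysis, so I first checked the Power Estimate inputs reused below. The standardised difference is (2.4 − 0.9)/1.7 = 0.88. With 50 per arm and two-sided 0.05, power for a difference of 1.5 with SD 1.7 is 99.3% (normal) or 99.2% (t), against a stated figure above 99%. The detectable difference at 80% power is 0.95 units (normal) or 0.96 (t), against the stated 0.96. Both reproduce.

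**2. Which interactions are planned.**

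| Variable | Main effect or covariate | Interaction with group |
|---|---|---|
| Race | Yes (Aims 1 and 2; Aim 3) | Yes (Aim 3) |
| Age, number of comorbidities | Yes (Aims 1 and 2) | None stated |
| Other demographics | Not stated | None stated |
| Baseline SPPB | Yes (baseline control) | None stated |

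The word mediation can be read in two ways. If it means an indirect effect, the method cannot answer the question posed. If it means a main-effect term, as the Aim 3 plan uses it for race, the variables enter only as covariates. Neither reading fits an interaction for age, comorbidity or baseline function.

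**3. Size of the artefact (illustration).** For a baseline variable X in SD units, the apparent mediated effect is the unadjusted minus the X-adjusted group difference, which equals b × (mean of X in WL-Protein − mean of X in WL-Control). Under randomisation the expected difference in means is zero, so the product has mean zero. Inputs:

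- SD of SPPB change 1.7 and true difference 1.5 (Power Estimate).
- 56 completers per arm (Study Arms).
- Correlation r between X and SPPB change: **assumed**, range 0.1 to 0.5. The documents give no value.

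If the slope were known, SD = 1.7 × r × √(2/56), and √(2/56) = 0.189:

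- r = 0.1: 0.032
- r = 0.3: 0.096
- r = 0.5: 0.161

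Estimating the slope adds some variability. Simulation (5,000 trials per row) gives:

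| r | Mean | SD | 95% range | Beyond ±0.15 units (10% of 1.5) |
|---|---|---|---|---|
| 0.1 | 0.00 | 0.045 | −0.10 to +0.10 | 1% |
| 0.3 | 0.00 | 0.100 | −0.21 to +0.20 | 13% |
| 0.5 | 0.00 | 0.164 | −0.33 to +0.32 | 35% |

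The apparent effect correlates 0.73, 0.96 and 0.99 with the observed imbalance in X. At 84 per arm, the other group size in the protocol, the SDs are 0.034, 0.080 and 0.132.

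**4. Race.** With race split equally within each arm, the same calculation gives exactly 0.

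**The case against.** The strongest reply is that the plan uses the word loosely. It specifies no indirect effect and no product of coefficients, and the one place that shows its meaning equates mediating with a main effect. Read that way, the analysis is ordinary covariate adjustment, which is legitimate. This stands as far as it goes: one cannot say that the plan commits to reporting indirect effects. It does not rescue the analysis, because adjustment does not test whether change depends on baseline status.

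Imbalance is also partly dealt with. Age, race and comorbidity count are examples of prespecified covariates, and sensitivity analyses for group imbalance are planned. The artefact in the illustration would therefore not shift the primary estimate for a variable already in the model.

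A reader might infer that race has the same defect. The documents do not support that. The race-by-group interaction is planned for SPPB and for the secondary outcomes, and randomisation is blocked on race, so imbalance at randomisation should be close to nil. Only the label is wrong.

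A reader might also infer that adherence is the only possible mediator. That is too absolute. Weight appears in the demographics list and is measured weekly, so weight change after randomisation is a candidate. Comorbid variables are not explicitly called baseline either, although the schedule lists no comorbidity count after entry.

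**Conclusion.** The point holds as a minor correction to an exploratory analysis. For demographic and comorbid variables fixed before randomisation, mediation of the group effect has expected value zero, and the moderation question posed in the next sentence has no planned test except for race.

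The illustrative SD of 0.05 to 0.16 SPPB units rests on the assumed correlations, an unblocked variable, and dropout that does not itself unbalance the arms; selective dropout could add imbalance among those analysed. These SDs should not be read as bias in the trial's main result. The primary 2-df test, the sample size and the power are untouched.

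**What to change.** - **Analysis Plan for the parent protocol (Aims 1 and 2).** Replace mediation by demographic and comorbid variables with group-by-variable and group-by-time-by-variable interactions. Include baseline functional status, which the plan's own rationale names. List the variables in advance.
- **Label these tests exploratory and low-powered.** For an evenly split binary moderator with 28 per cell and SD 1.7, the interaction detectable at 80% power is about (1.96 + 0.84) × 1.7 × √(4/28) = 1.80 units (normal approximation, one time point). That exceeds the 1.5-unit pilot effect. Report estimates with confidence intervals.
- **Restrict mediation to post-randomisation measures** such as adherence, and state the model and its assumptions.
- **Analysis Plan (Aim 3).** Call the race main effect prognostic, and keep the planned race-by-group interaction as the moderation test.

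The cost is a change of wording and a different exploratory model on data already being collected. No visits, measurements or participants are added.

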Late-life obesity is one of the greatest health care challenges facing VHA as large numbers of Veterans approach old age. Obesity's impact on physical function is under-studied in many of those at highest risk for frailty, including obese older men with prediabetes. Thus, the proposed research addresses an important gap in the evidence needed to guide obesity treatment and diabetes prevention in older Veterans. It is based on evidence that balanced protein feeding benefits muscle function and the hypothesis that, in concert with moderate calorie restriction, it will provide an effective obesity treatment that preserves muscle while reducing body fat and improving glucose handling. The research also includes careful documentation of study participation and intervention adherence in order to analyze differential responses due to race, socio-economic status, and other factors unique to older Veterans. This will be the first randomized controlled trial to examine balanced feeding of a higher protein diet during a period of metabolic challenge (caloric restriction) in those with prediabetes and the first study to look at racial differences in response of obese older men to this regimen. There are very few studies of racial differences in response to obesity interventions.

Thus, the importance of our exploratory aim for understanding the unique challenges facing obese black men in later life and the potential benefit of new obesity treatments for them is underscored.

Specific Aims

Aim 1: To compare a balanced, higher-protein weight loss diet to a control weight loss diet with regards to the primary outcome of physical function.

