Secondary outcomes: muscle quality (the ratio of knee extensor peak torque to thigh muscle area (cm²) assessed by using compute tomography (CT) (in Nm/cm²); insulin sensitivity, Air Displacement Plethysmograph (BodPod) to measure body weight, lean mass, and body fat; waist circumference, function tests (handgrip, 8-ft up and go, 30-sec chair stand, 6-min walk); physical activity (Actigraph); recent falls and fear of falling, diet adherence and nutritional adequacy; activities of daily living and independent activities of daily living; and quality of life and mood indicators (SF-36 Health Status questionnaire, Profile of Mood States questionnaire, and Pittsburgh Sleep Quality Index).

Measurement/Procedure	Time Points ¹	Method
Diet/Intervention		
Body weight	Weekly	Same scale, light clothing and no shoes, measured to nearest 0.1 kg
3-day diet record; Daily food journal (Adherence)	0, 3, 6 months	3-day diet record by multiple pass; analyzed Food Processor (Version 10.13, 2013; ESHA Research); Daily food journal assessed by RD
Protein checklist	Monthly	RedCap analysis
Actigraph, Axis accelerometer (activity counts, step counts, physical activity intensity)	0, 3, 6 months; 7	Actigraph WGT3X-BT activity counts at 1-s epoch from three orthogonal axes at 30 Hz sampling frequency. We

¹ Participants who are consented after 10/1/2023 will participate in a shortened version of the study. Data will be collected at month 0 and month 3 as outlined in this table. Body weights will still be collected weekly and the Nutrition and Exit questionnaires will be conducted at 3 months.

	days each time point	have been using Actigraphs in previous studies and therefore have not included in the budget.
Nutrition Questionnaires	0 months	Food Security Questionnaire
Nutrition Questionnaires	0, 6 months	Nutrition Literacy Questionnaire
Intervention Evaluation	6 months	Exit Questionnaire
Tissue, metabolic analyses		
Routine chemistries, blood	0, 3, 6 months	Metabolic Panel (LabCorp)
Function, body composition		
SPPB (6, 64, 66)	0, 3, 6 months	Balance (side-by-side, semi-tandem, tandem), gait speed (4-meter timed walk), strength (chair stands).
6-minute walk test (aerobic endurance)	0, 3, 6 months	As many walking laps as possible in six minutes between cones placed 40 meters apart
8-ft Up and Go: (agility/dynamic balance)	0, 3, 6 months	Begins seated. On word 'go' stands, walks around a cone 8 feet away, returns to seated.

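### A positive correlation between two outcome trajectories, pooled over arms, cannot support a generalised intervention effect, and for mixed-direction pairs joint benefit would give a negative sign

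*Combined protocol and SAP*

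**What the plan says.** The rule is in *Data Analysis and Statistical Considerations*, under *Analysis Plan for the parent protocol (Aims 1 and 2)*, after the main model, mediation and the shape of change over time. The step pools the arms: "we will assess whether the trajectories of change, irrespective of group assignment, are similar for individuals". The hypothesis is broad: "We further hypothesize that all these variables will change in the same pattern". The reading is then fixed by sign: "A positive correlation between the trajectories for any two outcomes will indicate that the subjects changed similarly for the 2 outcomes". Such a result is to give "additional support for the notion that the intervention had a generalized effect across the outcomes". A more cautious remark follows: "Significant correlations would perhaps indicate mechanistic/causal linkage between variables over time".

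The outcomes do not share one direction of benefit. *Background and Significance* describes the goal as an "effective obesity treatment that preserves muscle while reducing body fat and improving glucose handling". The secondary outcome list uses BodPod "to measure body weight, lean mass, and body fat; waist circumference" and sets these beside function tests. No section orients the outcomes or says how an expected negative correlation is to be read.

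**The concern.** A generalised effect is a statement about means: the intervention moved several outcomes in the beneficial direction. A correlation between individual changes answers a different question, namely whether men who changed more on one outcome also changed more on another. The plan uses an answer to the second question as support for the first.

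Two kinds of error follow. Both arms receive calorie restriction, group support and exercise, so changes may well be associated within men even if the diets are equivalent; the rule would then report support for an effect that is absent. Conversely, a real effect on both outcomes may leave the correlation weak. For pairs in which one outcome improves by falling, it would make the correlation negative. At stake is the interpretation of a long list of secondary outcomes for which the plan makes no Type-I error adjustment.

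**Working it through.** **The plan's own figures.** No number is attached to the correlation rule. The nearest figures are in *Power Estimate*. The SPPB effect in the earlier study is (2.4 − 0.9)/1.7 = 0.88 SD, as stated. With 50 men per arm, the t-test detects 0.566 SD at 80% power, and 0.566 × 1.7 = 0.96 units, also as stated. I use 0.88 and 0.57 SD as effect sizes below.

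**Inputs.** N = 112 completers (*Design*), allocated 1:1; two-sided 0.05 (*Power Estimate*). The within-arm correlation ρ between two change scores, and the arm effect on the second outcome, are not in the documents. Both are assumptions.

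**Step 1: a shift common to all men.** Corr(X + a, Y + b) = Corr(X, Y). If every man gained the 0.9 SPPB units seen in the control arm of the earlier study, the correlation would be the same as if no one had gained anything. It therefore cannot show that the programme given to both arms moved a mean.

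**Step 2: a difference between arms.** The arm indicator has variance 0.25. With standardised arm effects d1 and d2, the pooled correlation is

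r = (ρ + 0.25·d1·d2) / √[(1 + 0.25·d1²)(1 + 0.25·d2²)].

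Arm effects enter only through the 0.25 terms, mixed with ρ. The chance of a significantly positive r, by Fisher z, is 1 − Φ(1.96 − atanh(r)·√109), with √109 = 10.44.

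**Step 3: results at N = 112.**

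| Scenario | ρ | r | Significantly positive |
|---|---|---|---|
| No arm effect on either outcome | 0.1 | 0.10 | 18% |
| No arm effect | 0.2 | 0.20 | 56% |
| No arm effect | 0.3 | 0.30 | 90% |
| No arm effect | 0.5 | 0.50 | about 100% |
| Benefit of 0.88 SD on both, higher is better for both | 0 | 0.16 | 40% |
| Benefit of 0.57 SD on both, higher is better for both | 0 | 0.08 | 12% |
| Benefit of 0.88 SD on one, harm of 0.88 SD on the other, higher is better for both | 0.5 | 0.26 | 78% |
| Benefit of 0.88 SD on both, one improving by falling | −0.3 | −0.41 | 0% (negative in 99.6%) |

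Examples. For ρ = 0.1: atanh(0.1) × 10.44 = 1.05, and 1 − Φ(1.96 − 1.05) = 18%. For the fifth row: 0.25 × 0.88² = 0.1936, r = 0.1936/1.1936 = 0.16, chance 40%. For the last row: (−0.3 − 0.1936)/1.1936 = −0.41.

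Simulation with 20,000 runs, for the null rows at ρ = 0.3 and 0.5, both ρ = 0 rows and the last row, agrees to within about one percentage point. At N = 100, the size used in *Power Estimate*, the null rows at ρ = 0.2 and 0.3 become 52% and 86%.

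**Step 4: does aligning direction repair the rule?** Reverse-scoring the falling outcome in the last row turns r from −0.41 to +0.41, significantly positive in 99.6%. The null rows do not change: at ρ = 0.3 there is still a 90% chance of apparent support with no arm effect. Alignment cures the sign and leaves the inference invalid.

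**The case against.** The strongest reply is that little rests on this step. Arm effects are tested for each outcome by the group and group-by-time terms of the mixed model. The correlations come last, are offered only as additional support, and the causal reading is qualified. This stands, and it sets the severity.

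Several stronger readings are tempting but not supported:

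- A reader might infer that a negative correlation counts against a generalised effect. The plan never says so. It defines what a positive correlation means and leaves the negative case open. The sign problem is also confined to mixed-direction pairs.
- A reader might infer that the plan uses the correlations to claim an advantage for the higher-protein diet. The sentence refers to the intervention, a word the protocol also uses for components given to both arms. The objection holds under either meaning: Step 1 covers the shared programme and Step 2 the arm contrast.
- A reader might infer that the rule almost always signals support. That needs a within-arm correlation near 0.5; at 0.1 the figure is 18%.
- A reader might class mood and sleep scores as improving by falling. The documents do not state their scoring direction. Body weight, body fat and waist are clear, and they suffice.
- A reader might treat lean mass as improving only by rising. The protocol speaks of preserving it and notes that lean mass can be lost with weight. Weight and lean-mass changes may then correlate positively, so blanket reverse-scoring would not make a positive sign mean joint benefit for every pair.

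**Conclusion.** The point holds in this form: the step from a positive pooled trajectory correlation to support for a generalised effect is invalid, and the rule has no convention for pairs whose benefits run in opposite directions. It can signal support with no arm effect, miss a real effect on both outcomes, and be positive when one outcome benefits and the other is harmed. How often depends on within-arm correlations that the documents do not give, so the percentages are a range over assumptions and not a forecast. The effects of 0.88 and 0.57 SD are the plan's SPPB figures; applying them to a second outcome is also an assumption. The logical point depends on none of these values. This is a low-severity correction to a supportive secondary analysis.

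**What to change.** In the parent analysis plan for Aims 1 and 2:

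- **(a)** Delete the statement that a positive correlation supports a generalised intervention effect. Report trajectory correlations within arm, or adjusted for arm, as descriptive association only.
- **(b)** State in advance the direction of benefit for each outcome and the expected sign for each pair. Weight, body fat and waist follow from the documents; the sponsor should state the direction for the remaining scales and for lean mass.
- **(c)** Base any statement about a generalised effect on the between-arm estimates already planned for each outcome, shown together on a standardised, direction-aligned scale. A global test of group is optional.

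The cost is a few sentences of analysis-plan wording, a table of directions and some recoding. No new data are needed.
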